1.2 Approval

REPRESENTATIVES OF TAKEDA

This study will be conducted with the highest respect for the individual participants in accordance with the requirements of this non-interventional study protocol and also in accordance with the following:

The ethical principles that have their origin in the Declaration of Helsinki [32]; Guidelines for Good Pharmacoepidemiology practices (GPP) [19]; Guidelines on Good Pharmacovigilance Practices (GVP) [20]; All applicable laws and regulations, including, without limitation, data privacy laws and regulations.

SIGNATURES

PI

Pr

2 Study summary

Title of the Study

INTENT - International, Multicentre, Non-Interventional Study To Evaluate Disease Control And Treatment Pattern In Patients With Moderate To Severe Inflammatory Bowel Disease In Real Life Practice.

Study sites

Number of sites: about 35 investigational sites from the Russian Federation, the Republic of Belarus and the Republic of Kazakhstan.

Identification of centres for participation in the study will be based on the assessment of medical centres and hospitals that conduct clinical observation of patients with Inflammatory Bowel Disease (IBD).

Objectives

The purpose of this study is to collect information regarding the real life practice of moderate to severe IBD management in the Russian Federation, the Republic of Belarus and the Republic of Kazakhstan: to document treatment patterns and treatment outcomes in patients with IBD including particularly on the use of available biologic therapies.

Primary objective:

- To characterize the treatment patterns associated with biologics agents use or non-biological therapy (i.e. 5-ASA, immunosuppressive agents (including azathioprine (AZA), 6-mercaptopurine (6-MP), methotrexate (MTX), cyclosporine A), corticosteroids) in patients with moderate to severe Ulcerative Colitis (UC) and moderate to severe Crohn's Disease (CD).

Secondary objectives:

- To characterize patients treated with biologics or/and non-biological treatment (i.e. 5-ASA, immunosuppressive agents (including azathioprine (AZA), 6-mercaptopurine (6-MP), methotrexate (MTX), cyclosporine A), corticosteroids) in terms of demographics, medical, and treatment histories;
- To evaluate and describe the implementation and achievement of Treat-to-target (T2T) goals in real-world clinical practice in moderate to severe IBD patients treated by biological and non-biological therapy during 2 years before enrolment and 1 year observational period after enrolment by treatment type 1) to assess the extent to which proposed Treat to Target goals are achieved in moderate to severe UC/CD patients 2) to describe how and when UC/CD disease activity is assessed 3) to evaluate the potential challenges to achieving T2T targets during routine care ;

- Establish the impact on healthcare resources utilization for patients with moderate to severe UC and CD

Safety Objective:

- To describe the incidence of real-world safety data occurred during 12-months treatment period within routine clinical practice by treatment type (biologics or non-biological IBD therapy) and treatment history (biologic treatment naïve or with prior biological treatment).

Exploratory objective:

- To assess TB in moderate to severe IBD patients receiving biologics and/or non-biological treatment.

Methodology

Study Design: International, multicentre, non-interventional retrospective and prospective study.

Study plan: The definition of a Non-Interventional study is provided in Guidelines for Good Pharmacovigilance Practices (GVP) of Eurasian Economic Commission No. 87 [20]. During participation in the study patients are observed according to the local routine practice. The assignment of a particular therapeutic strategy to the patient including all diagnostic procedures is decided in accordance with Clinical recommendations of the Russian gastroenterological association and association of coloproctologists of Russia on the diagnosis and treatment of ulcerative colitis and Crohn's disease; Clinical Protocols of diagnosis and treatment of ulcerative colitis and Crohn's disease in the Republic of Kazakhstan and Clinical Protocol "Diagnosis and treatment of patients with diseases of the digestive system", Appendix 3 in the Republic of Belarus and local routine practice [6-10]..

Number of patients

Approximately 2000 patients will be enrolled in the study.

Diagnosis/Disease/Condition and main criteria for inclusion

Inclusion criteria:

1. Male and female patients 18 years or older by the time of enrolment
2. Confirmed diagnosis of Crohn's disease or ulcerative colitis for at least 2 years prior to enrolment in the study.
3. The presence of a moderate to severe IBD flare at the time of enrolment or in patient anamnesis within 2 years before enrollment treated with steroids or/ and immunosuppressive agents or/ and biologic therapy. IBD flare(s) must be confirmed in the source documentation.
4. Current treatment with steroids or/ and immunosuppressive agents or/ and 5-ASA or/ and biologic therapy
5. Written informed consent, signed before the participation in the study begins.

Exclusion criteria:

Any patient who meets any of the following criteria will not be qualified for entry into the study:

1. Current or previous (within the last two years) indeterminate or not classified colitis.
2. Changing of IBD type in anamnesis (i.e. from UC to CD, etc.) within the last two years.
3. Current, previous (within the last two years) or planned (for the next one year) participation in interventional clinical trial.
4. Presenting of mental incapacity, unwillingness or language barriers precluding adequate understanding or cooperation.
5. Any other condition, which on the opinion of the investigator may impact the patient's participation in the study.
6. Patient received previous treatment with biologic therapy/immunosuppressive agents for conditions other than IBD ever in their lifetime.

Duration of data collection per patient

Data collection per patient will be carried out within the framework of the routine practice. Due to the non-interventional study design it's not possible to appoint exact times for the study visits, although it is expected that the period of observation will be approximately 12 months. The frequency of the visits will be assigned by each physician according to their routine practice. It is anticipated that the patients will visit their physician at least every 6 months; information for the study will be collected from 3 patients' visits to the physician.

Criteria for evaluationPopulation descriptors

The main assessments, which will be performed in the study, are presented in the table below.

Assessment / Procedure	Retrospective data collection*	Baseline visit (V1, Day 1)	Observational visit (V2, Month 6)	Final visit (V3, Month 12)
Informed consent		X		
Patients' eligibility assessment: Inclusion/exclusion criteria		X		
Date of visit		X	X	X
Demographics data		X		

Disability		X		
Physical examination		X	X	X
Medical history / Concurrent medical conditions	X	X		
History of IBD	X	X		
IBD family history		X		
IBD assessment	X	X	X	X
Disease activity data		X	X	X
IBD status		X	X	X
Laboratory and instrumental evaluation of IBD **	X	X	X	X
IBD treatment	X	X	X	X
Healthcare resources utilization	X	X	X	X
Concomitant treatment		X	X	X
Physician Survey		X		X
Adverse events			X	X

* Retrospective data within two years before of patient enrolment in the study will be collected at Visit 1 after the signing of the informed consent form

**All examinations (laboratory tests and instrumental exams) are done in accordance with clinical routine practice and physician's decision. All examinations results should be registered in electronic CRF only if they are done in routine practice.

Outcomes

The following outcomes will be evaluated in this study separately for UC and CD patients, within each group for subgroups of patients on biologic and non-biological therapy. Study outcomes will be analysed separately for the patients achieved and not achieved clinical remission during the study.

Primary outcomes:

- Distribution of treatment patterns used in patients with moderate to severe UC and with moderate to severe CD treated with biologics. Treatment patterns will be evaluated within 2 years before enrolment – retrospective data and one year after enrolment- prospective data and will include name and type of drug (original product or biosimilar) and treatment regimen including modifications.
- Distribution of treatment patterns used in patients with moderate to severe UC and with moderate to severe CD treated with non-biological treatment. Treatment patterns will be

evaluated within 2 years before enrolment – retrospective data and one year after enrolment-prospective data and will include treatment regimen including modifications.

Secondary outcomes:

- Distribution of socio-demographic variables in patients with moderate to severe UC/ CD treated with biologics or/and non-biological treatment.
- Distribution of clinical variables in patients with moderate to severe UC/ CD treated with biologics or/and non-biological treatment. Clinical characteristics include family history of IBD, smoking habits (no smoker, ex-smoker and current smoker), medical history comorbidities, disease characteristics (age of disease onset, location of disease, clinical course, disease severity, intestinal and systemic (extraintestinal) manifestations, complications in history and during the study observational period, etc).
- Description of methods used for documentation of disease activity in routine practice (incl. clinical, endoscopic, lab, histological), and frequency of objective CD/UC disease activity assessment using different methods.
- Percentage of moderate to severe IBD patients achieved clinical and combined clinical and endoscopic remission (based on T2T definitions).
 - Percentage of patients with moderate to severe IBD with at least one episode of failure of biological therapy or/and non-biological therapy (e.g., dose escalation of biologics, switching to another therapy, IBD-related surgery, medication augmentation).
- Patterns of treatment decisions\actions made after making the clinical assessment of IBD activity (incl. therapeutic de-escalation, escalation, without changes) depending on scenario of achievement /non-achievement of T2T treatment goals.
- Challenges of implementing a T2T strategy in UC and CD in real clinical practice (incl. clinicians related factors, patient related factors, disease related factors).
- Healthcare resources utilization for patients with moderate to severe UC/ CD: hospitalizations due to complications, IBD related surgeries, disability determination (frequency, percentage of UC and CD patients, who used these healthcare resources) within 2 years before enrolment and during 12-months observational period

Percentage of UC and CD patients with surgical treatment in 2 years history and during 12-months observational period in frames of this study: indications, types of surgeries, complications.

Safety outcome:

- Patient incidence and type of adverse drug reactions related to IBD treatment occurring during 12-months treatment period within routine clinical practice by treatment type (biologics or non-biological therapy) and treatment history (biologic treatment naïve or with prior biological treatment);
- Patient incidence and type of serious adverse events related to IBD treatment occurring during 12-months treatment period within routine clinical practice by treatment type (biologics or non-biological therapy) and treatment history (biologic treatment naïve or with prior biological treatment).

Exploratory outcomes:

- Number of moderate to severe UC and CD patients with TB positive tests results/active TB before start of biological therapy.
- Number of moderate to severe UC and CD patients with TB reactivation/occurrence in frames of this study by treatment type (biologics or/and non-biological treatment).

Statistical methods

All data from patients enrolled in this study will be analysed. Information on CD and UC patients will be presented separately. Also, analysis will be performed separately by therapy subgroups (patients receiving non-biological therapy and patients receiving biological therapy). Due to complexity of treatment regimen a manual review can be used to define treatment subgroup for each patient.

A descriptive analysis approach will be used to analyse the data and the study outcomes for the different study subgroups.

Descriptive statistics will include summary tables (n, mean, median, standard deviation, minimum and maximum, lower and upper quartile for continuous variables and n, frequency and percentage for categorical values). Proportion will be assessed together with 95% confidence interval, if applicable. Cross tabulations will be used to present study outcomes by the corresponding subgroups, when required. Time to event will be described with Kaplan-Meier estimates. Median time to event will be presented together with the lower and upper quartiles. Baseline and retrospective data will be used to describe the patient population and will be tabulated separately.

The number and percentage of patients who have reached remission while in the study will be presented. Selected outcomes will be reported separately for those who have reached remission and those who haven't. Mayo and HBI scores data will be analyzed according to the scales definitions.

Laboratory data will be reported in terms of frequency and percentage of abnormal findings.

In general, all data will be listed, sorted by type of disease (UC and CD), site and patient number, and when appropriate by visit number within patient.

3 Table of Contents

Contents

1	Administrative information	2
1.1	Contacts	2
1.2	Approval	3
2	Study summary	4
3	Table of Contents	10
4	List of Abbreviations and Definition of Terms	14
4.1	List of Abbreviations	14
4.2	Definition of Terms	16
4.3	IBD activity assessment	17
4.4	Treat to target approach in IBD treatment	17
5	Introduction	17
5.1	Background	17
5.2	Rationale	18
6	Study Objectives and outcomes	19
6.1	Study objectives	19
6.2	Study outcomes	20
7	Study Administrative Structure	21
7.1	Steering Committee	21
7.2	Study Sites	22
7.3	Sponsor Personnel	22
7.4	Contract Research Organisation	23
7.5	Essential Documents	24
8	Ethical and Legal aspects	24
8.1	Ethical conduct of the Study	25
8.2	Independent Ethics Committee	25

4.1 List of Abbreviations

ADR:	Adverse Drug Reaction
AE:	Adverse Event
ALT:	Alanine Aminotransferase
AST:	Aspartate Aminotransferase
BMI:	Body Mass Index
CA:	Competent Authority
CD:	Crohn's disease
CER:	Clinical and endoscopic remission
CIS:	Commonwealth of Independent States
CR:	Clinical remission
CRF:	Case Report Form
CRO:	Contract Research Organisation
CRP	C-reactive protein
CV:	Curriculum Vitae
DMP:	Data Management Plan
DSO:	Drug Safety Officer
EC:	Ethics Committee
eCRF:	electronic Case Report Form
ESR:	Erythrocyte Sedimentation Rate
EU:	European Union
FPFV:	First Patient First Visit
FPLV:	First Patient Last Visit (end of enrolment)
GCP:	Good Clinical Practice
GEP:	Good Epidemiological Practice
GI:	Gastroenterologist
GPP:	Good Pharmacoepidemiology Practices
GVP:	Good Pharmacovigilance Practices
HCRU:	Health care resource utilisation
IBD:	Inflammatory bowel disease

ICF:	Informed Consent Form
ICH:	International Conference on Harmonisation
IDS:	International Drug Safety
IEC:	Independent Ethics Committee
INN:	International Nonproprietary Name
IRB:	Institutional Review Board
LEC:	Local Ethics Committee
LPLV:	Last Patient Last Visit
MedDRA:	Medical Dictionary for Regulatory Activities
NIS:	Non-interventional study
PSUR:	Periodic Safety Update Report
QA:	Quality Assurance
RB:	the Republic of Belarus
RK:	the Republic of Kazakhstan
RF:	the Russian Federation
SAP:	Statistical Analysis Plan
SADR:	Serious Adverse Drug Reaction
SAE:	Serious Adverse Event
SmPC:	Summary of Product Characteristics
SD:	Standrad Deviation
SDV:	Source Data Verification
SPC:	Summary of Product Characteristics
TB:	Tuberculosis
TNF α :	Tumor Necrosis Factor- α
T2T:	Treat to Target
UC:	Ulcerative colitis
WBC:	White blood cells
WHO:	World Health Organization

4.2 Definition of Terms

Inflammatory bowel disease (IBD) - a group of chronic, often relapsing, immunologically-mediated gastrointestinal disorders: Crohn's disease (CD) and ulcerative colitis (UC). Crohn's disease may involve any portion of the length of the gastrointestinal tract from mouth to anus in a transmural fashion from mucosa to serosa whereas ulcerative colitis primarily affects colonic mucosa and submucosa.

IBD flare - a flare of symptoms in a patient with established CD/UC who is in clinical remission, either spontaneously or after medical treatment. Relapse should be preferably confirmed by laboratory parameters, endoscopy or imaging in clinical practice. The definition of IBD flare (including severity) will be in accordance with Clinical recommendations of the Russian gastroenterological association and association of coloproctologists of Russia on the diagnosis and treatment of ulcerative colitis and Crohn's disease; Clinical Protocols of diagnosis and treatment of ulcerative colitis and Crohn's disease in the Republic of Kazakhstan and Clinical Protocol "Diagnosis and treatment of patients with diseases of the digestive system", Appendix 3 in the Republic of Belarus and local routine practice [6-10].

IBD is a chronic condition that is characterized by intermittent periods of active disease (relapses) and little or no disease activity (remission). The duration and severity of the active period vary widely from person to person. The goal of treatment of IBD is to induce and maintain remission for better outcomes of the disease.

IBD remission – a resolution of symptoms (clinical remission) and mucosal inflammation (endoscopic remission). The definition of IBD remission will be in accordance with Clinical recommendations of the Russian gastroenterological association and association of coloproctologists of Russia on the diagnosis and treatment of ulcerative colitis and Crohn's disease; Clinical Protocols of diagnosis and treatment of ulcerative colitis and Crohn's disease in the Republic of Kazakhstan and Clinical Protocol "Diagnosis and treatment of patients with diseases of the digestive system", Appendix 3 in the Republic of Belarus and local routine practice [6-10].

Biologics dose escalation will include any increase in dose, frequency, or both;

Augmentation with non-biological therapy will be defined as starting a new non-biological drug or increase in dose/frequency of the concurrent non-biological drugs with biological therapy. Non-biological therapies included aminosalicylates, immunomodulators, and corticosteroids;

Switching will be defined as a subset of initial biologic agent discontinuers who initiated another biological therapy;

IBD-related surgery will include but not be restricted to colectomy, ostomy (colostomy or ileostomy), fistula repair, abscess repair, and strictureplasty.

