6.2 Study outcomes

The following outcomes will be evaluated in this study separately for UC and CD patients, within each group for subgroups of patients on biologic and non-biological therapy. Study outcomes will be analysed separately for the patients achieved and not achieved clinical remission during the study.

Primary outcomes:

- Distribution of treatment patterns used in patients with moderate to severe UC and with moderate to severe CD treated with biologics. Treatment patterns will be evaluated within 2 years before enrolment – retrospective data and one year after enrolment- prospective data and will include name and type of drug (original product or biosimilar) and treatment regimen including modifications.
- Distribution of treatment patterns used in patients with moderate to severe UC and with moderate to severe CD treated with non-biological treatment. Treatment patterns will be evaluated within 2 years before enrolment – retrospective data and one year after enrolment- prospective data and will include treatment regimen including modifications.

Secondary outcomes:

- Distribution of socio-demographic variables in patients with moderate to severe UC/ CD treated with biologics or/and non-biological treatment.
- Distribution of clinical variables in patients with moderate to severe UC/ CD treated with biologics or/and non-biological treatment. Clinical characteristics include family history of IBD, smoking habits (no smoker, ex-smoker and current smoker), medical history comorbidities, disease characteristics (age of disease onset, location of disease, clinical course, disease severity, intestinal and systemic (extraintestinal) manifestations, complications in history and during the study observational period, etc.).
- Description of methods used for documentation of disease activity in routine practice (incl. clinical, endoscopic, lab, histological), and frequency of objective CD/UC disease activity assessment using different methods.
- Percentage of moderate to severe IBD patients achieved clinical and combined clinical and endoscopic remission (based on T2T definitions).
- Percentage of patients with moderate to severe IBD with at least one episode of failure of biological therapy or/and non-biological therapy (e.g., dose escalation of biologics, switching to another therapy, IBD-related surgery, medication augmentation).

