12.6 Treatments to be documented in the study

12.6.1 IBD treatment

Due to non-interventional design of the study, the decision about particular IBD treatment strategy to the patient is taken by treating physician. All IBD medications are not provided by Sponsor.

Following medications for IBD treatment should be registered in eCRF; 5-ASA, immunosuppressive agents (including azathioprine (AZA), 6-mercaptopurine (6-MP), methotrexate (MTX), cyclosporine A), corticosteroids and biologics.

The following data should be documented for steroids:

- INN name;
- release form;
- Route of administration
- Indication
- start date;
- initial and maximum daily dose;
- funding source;
- dose, if continued / end date and the reason for modification/ discontinuation, if discontinued.

The following data should be documented for 5-ASA, immunosuppressive agents:

- INN name;
- release form;
- Route of administration
- Indication start date;
- daily dose;
- funding source;
- continued / end date and the reason for modification/discontinuation.

The following data should be documented for biologics:

- trade and INN name;
- Indication start date;
- treatment regimen (induction or supportive care);
- dosage regimen;
- Route of administration
- funding source;
- continued / end date and the reason for modification/discontinuation.

If a physician takes a decision to change something from the above it must be documented in the eCRF.

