15.2.1. Summary of study data

All continuous variables will be summarised using the following descriptive statistics: n (non-missing sample size), mean, standard deviation, median, 25 percentile, 75 percentile, maximum and minimum. The frequency and percentages (based on the non-missing sample size) of observed levels will be reported for all categorical measures. For variables marked “binary” exact (Clopper-Pearson) 95% confidence intervals will be calculated where appropriate. For categorical variables with more than 2 categories 95% confidence intervals will be calculated using Goodman’s method [33].

In general, all data will be listed, sorted by site and patient, and when appropriate by visit number within patient. All summary tables will be structured with a column for each treatment pattern in the pre-defined order and will be annotated with the total population size relevant to that table/treatment pattern, including any missing observations.”

Patient Disposition

Data regarding how many patients reached the various stages of the study, how many dropped out, discontinued the treatment and for what reasons (death, ADRs, treatment failure, withdrew consent, lost to follow-up) will be presented for each subgroup and for study in bulk. Standard CONSORT diagram describing study patient flow will be provided.

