15.4 Determination of Sample Size

The primary objective of this study is to obtain the accurate and comprehensive information regarding the treatment regimens used in patients with moderate to severe UC and CD flare within routine clinical practice in Russia, Belarus and Kazakhstan. For this purpose, sample size should be large enough to contain essential number of patients with different therapy options.

One of the key secondary objectives is to assess the percentage of Ulcerative Colitis (UC) and Crohn's Disease (CD) patients with at least one episode of failure of non-biological therapy with immunosuppressive agents or biological therapy registered within 12 months from the beginning of moderate to severe IBD flare. Based on literature data, up to 20-40% of IBD patients

experience failure of TNF antagonist therapy initially, and in 10-20% of patients per year loss of response is observed.

Assuming the percent of patients receiving biological therapy in the study population is 40%, about 40% proportion of CD patients [5, 6] and that 40-50% of the patients on biological therapy will have at least one episode of treatment failure during 12 months, enrolment of 2000 patients totally will be sufficient to estimate the proportion of patients on biological therapy with treatment failure during the 12 months of observation with acceptable precision in both UC and CD subgroups ($\pm 5.8\%$ for the smaller subgroup of CD patients and the assumed failure rate of 50%). The table below shows 95% confidence intervals for the estimated proportions of 40%, 50% and different sample size values. For other, more prevalent subgroups (CD patients on non-biological therapy, UC patients on each type of therapy) the proposed sample size will also allow to estimate proportion of patients with treatment failure with same or higher precision.

The total number of patients to be enrolled	The number of CD patients on biotherapy*	The number of CD patients in the analysis assuming 10% drop-out	Assumed failure rate of biotherapy**	
			40%	50%
2000	320	288	34.3-45.7%	44.2-55.8%
2500	400	360	34.9-45.1%	44.8-55.2%
3000	480	432	35.4-44.6%	45.3-54.7%
3500	560	504	35.7-44.3%	45.6-54.4%
4000	640	576	36.0-44.0%	45.9-54.1%
4500	720	648	36.2-43.8%	46.2-53.8%
5000	800	720	36.4-43.6%	46.3-53.7%

* Assuming the percent of patients receiving biotherapy is 40% among the study population. The precision (95% CI) is shown for the smaller subgroup of CD patients (approximately 40%).

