## 6 MAIN ASSESSMENTS

### 6.1 Endpoints (outcomes)

**Primary endpoint (outcome):** Distribution of treatment patterns used in patients with moderate to severe UC and with moderate to severe CD treated with biologics. Treatment patterns will be evaluated within 2 years before enrolment – retrospective data and one year after enrolment – prospective data and will include:

- trade and INN name;
- original medication or biosimilar medication;
- dosage regimen (dose, route and frequency);
- duration of each dose regimen;
- presence of treatment modifications/discontinuation;
- funding source;
- reason(s) for modification/discontinuation of IBD medicine treatment;

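### The treatment-failure outcome takes no account of the recorded reason for a treatment change, so changes made for reasons other than efficacy can be counted as therapy failure

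*Protocol*

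**What the plan says.** The outcome in Protocol 6.2 is the percentage of patients with at least one episode of failure of biological and/or non-biological therapy. It is explained only by a list: "e.g., dose escalation of biologics, switching to another therapy, IBD-related surgery, medication augmentation". SAP 6.1 repeats the list, and SAP 8.1.3 tabulates it by Visits 1, 2 and 3. Neither adds a condition.

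Protocol 4.2 defines the components:
- Escalation: "Biologics dose escalation will include any increase in dose, frequency, or both".
- Switching: "Switching will be defined as a subset of initial biologic agent discontinuers who initiated another biological therapy".
- Augmentation: starting a new non-biological drug alongside a biologic, or raising the dose or frequency of one already given.
- Surgery: an open list of IBD-related procedures.

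The reason for change is collected. Protocol 12.6.1 asks, in near-identical words for each drug class, for "continued / end date and the reason for modification/ discontinuation", and also for the funding source. SAP 6.1 lists "reason(s) for modification/discontinuation of IBD medicine treatment", funding source and original-or-biosimilar status, but as descriptors of the primary treatment-pattern endpoint. No section links them to failure.

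Protocol 15.4 calls the failure percentage a key secondary objective and bases the sample-size precision on it.

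**The concern.** A percentage labelled as failure of therapy will be read as a measure of inadequate disease control. The documents mostly use the word that way. Protocol 15.2.1 lists treatment failure as one reason for stopping treatment, separate from adverse drug reactions. Protocol 15.4 introduces the planning rate with literature on TNF antagonists, in which patients "experience failure of TNF antagonist therapy initially, and in 10-20% of patients per year loss of response is observed". The components as defined also admit changes that have nothing to do with response. Funding is a foreseeable example, since its source is recorded for every drug.

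At stake is the interpretation of the figure on which the study's precision was justified. Such contamination is not reflected in the confidence interval, and a larger sample would not reduce it. It could also differ between agents. SAP 8.1.2 groups TNF inhibitors by trade name and vedolizumab by INN. If switching were derived from that coding, a brand change within one INN would register for the first group and not for the second.

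**Working it through.** **1. The plan's own precision.** Inputs from Protocol 15.4: 2000 patients, 40% on biologics, about 40% with CD, 10% drop-out.

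n = 2000 × 0.40 × 0.40 × 0.90 = 288.

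Half-width = 1.96 × √(p(1−p)/n):
- p = 0.40: 1.96 × √(0.24/288) = 5.7 points, giving 34.3–45.7%.
- p = 0.50: 1.96 × √(0.25/288) = 5.8 points, giving 44.2–55.8%.

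Both match the protocol table. The Clopper-Pearson intervals named for the analysis are nearly the same at n = 288: 34.2–45.8% and 44.1–55.9%. SAP 8.2 still argues from 3000 patients (±4.7 points at 50%); the protocol's 2000 is used here.

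**2. False positives alone.** Let p be the true response-related failure rate. Let q be the share of the remaining patients who have a qualifying change for another reason. The documents give no value for q, so a range is assumed.

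Reported rate = p + (1−p)q; excess = (1−p)q.

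| q (assumed) | p = 40%: reported (excess) | p = 50%: reported (excess) |
|---|---|---|
| 5% | 43.0% (3.0) | 52.5% (2.5) |
| 10% | 46.0% (6.0) | 55.0% (5.0) |
| 15% | 49.0% (9.0) | 57.5% (7.5) |
| 20% | 52.0% (12.0) | 60.0% (10.0) |

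The excess equals the planned half-width when q = half-width/(1−p): 5.66/0.60 = 9.4% for p = 40%, and 5.77/0.50 = 11.5% for p = 50%.

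**3. False negatives.** Two kinds of true failure trigger no drug-change event in the list: a non-responder who stops a biologic and starts no other, and a patient with uncontrolled disease whose therapy is left unchanged. Protocol 6.2 foresees the second, because it describes decisions without change when treat-to-target goals are not met. Let m be the share of true failures missed.

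Net bias = (1−p)q − pm, which is zero at m = (1−p)q/p. With q = 10%, that is m = 0.06/0.40 = 15% for p = 40% and m = 0.05/0.50 = 10% for p = 50%. Neither q nor m can be obtained from the documents, so neither can the sign of the net bias.

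**4. Which changes fit the text.**
- A move to a different biologic for funding or another non-efficacy reason meets the switching definition directly.
- A same-INN biosimilar substitution meets it only if a new brand counts as another biological therapy, which is not stated.
- A dose rise with body weight meets the escalation definition only if dose means the absolute amount; the unit is not stated.
- Augmentation has the same gap as switching and escalation.

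**The case against.** The strongest reply is that the documents never say that every such event is a failure. The list is introduced by e.g., Protocol 4.2 defines the component terms but not failure itself, and an illustrative list is not a counting rule. That stands, and it limits the point to what can be counted. The documents do not, however, contain any rule under which a listed event would not count.

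Other stronger readings are tempting and are not supported:
- A reader might infer that biosimilar substitution and weight-driven dose increases are failures under the plan. Both rest on undefined terms. Trade-name grouping in SAP 8.1.2 concerns treatment combinations and is nowhere applied to switching.
- A reader might infer that the reported rate is biased upward overall. Step 3 shows why that does not follow.
- A reader might infer that the 40–50% planning rate was derived from response-based literature. Protocol 15.4 cites that literature and then assumes 40–50%; no derivation is shown.

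There is partial mitigation. Reasons, funding source and product type are described with the primary endpoint. SAP 8.1.3 shows modifications, treatment changes and flares by period, and SAP 8.1.5 tabulates treatment changes due to adverse events. A reader could see that non-efficacy changes occurred, but could not remove them from the failure percentage. Protocol 15.2.4 admits that effectiveness cannot be fully evaluated, but that does not correct how this percentage is labelled.

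**Conclusion.** The point holds in limited form. As written, switches, dose or frequency increases and augmentation made for non-efficacy reasons can enter the key secondary failure percentage, because its components are defined by event and the recorded reason is not used. The amount is unknown. On the assumed range of 5–20% of non-failing patients, false positives alone would add 2.5–12 points, against a planned half-width of 5.7–5.8 points. The excess passes that half-width at about 9% (true rate 40%) to 12% (true rate 50%). Net bias is not established in either direction. The sample-size arithmetic is correct and is not affected. This is a worthwhile and inexpensive repair of a definition in a descriptive study; it does not undermine the design.

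**What to change.** In Protocol 4.2 and SAP 6.1 and 8.1.3:

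1. Use the recorded reason to split switching, dose or frequency increase, and augmentation into (a) inadequate response, lost response or flare; (b) intolerance or adverse drug reaction; (c) other non-efficacy reason; (d) reason missing.
2. Report failure as IBD-related surgery plus (a). Put (b) on its own line, so that a reader who regards intolerance as failure can add it. Report the all-reason percentage as well.
3. Since no imputation is planned, give the failure percentage twice, with (d) counted as failure and as non-failure.
4. Define switching at INN level for this outcome, so that a same-INN brand change is a pattern change and not a failure. State the dose unit used to identify an increase.

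The cost is definition wording and a derived variable from fields already in the eCRF, with no new data collection. Precision is essentially unchanged: with 288 patients the half-width cannot exceed 5.8 points. The downsides are that some reasons will be missing or coarse, and the headline rate may be lower. For an added drug, the reason may have to be taken from its indication, because the reason field refers to modification or discontinuation. SAP 8.5 requires the change and its justification to appear in the final report.
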